8.2 Time Period, Frequency, and Method of Detecting AEs and SAEs

All adverse events will be monitored for and recorded daily between recruitment and discharge from hospital (Usually 5+ days). Late adverse events will be assessed on follow up post laparotomy (Usually at approximately 4 weeks). This will be recorded on either the data collection tool or their electronic notes up to 2 months post procedure.

8.3 Recording of AEs and SAEs

When an AE/SAE occurs, it is the responsibility of the investigators to review all documentation (Including the electronic notes, laboratory, and diagnostic imaging reports) relative to the event. The investigator will then record all relevant information regarding an AE/SAE in to the case report form (CRF).

For each adverse event, start and stop dates, action taken, outcome, intensity and relationship to study product will be documented. For non-expected adverse events, not outlined above, the investigator will attempt to establish a diagnosis of the event based on signs, symptoms, and/or other clinical information. In the absence of a diagnosis, the individual signs/symptoms will be documented

8.4 Evaluating AEs and SAEs

8.4.1 Assessment of Intensity

The investigator will make an assessment of intensity for each AE and SAE reported during the study. The assessment will be based on the investigator's clinical judgement. The intensity of each AE and SAE recorded in the CRF should be assigned to one of the following categories:

Mild: An event that is easily tolerated by the Participant, causing minimal discomfort and not interfering with everyday activities.

Moderate: An event that is sufficiently discomforting to interfere with normal everyday activities.

Severe: An event which is incapacitating and prevents normal everyday activities.

8.4.2 Assessment of Causality

The investigators will attempt to assess the relationship between the procedure/local anaesthetic infusion and the occurrence of each AE/SAE. The investigators will use clinical judgment to determine the relationship. Alternative causes, such as natural history of the underlying diseases, concomitant therapy and other risk factors will be considered and investigated.

The causal relationship to the study product assessed by the Investigator will be assessed using the following classifications:

Not Related	In the Investigator's opinion, there is not a causal relationship between the study product and the adverse event.
Unlikely	The temporal association between the adverse event and study product is such that the study product is not likely to have any reasonable association with the adverse event.
Possible	The adverse event could have been caused by the study Participant's clinical state or the study product.
Probable	The adverse event follows a reasonable temporal sequence from the time of study product administration, abates upon discontinuation of the study product and cannot be reasonably explained by the known characteristics of the study Participant's clinical state.
Definitely	The adverse event follows a reasonable temporal sequence from the time of study product administration or reappears when study product is reintroduced.

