7.6 Unblinding Procedure

The patient can be unblinded after all subjective testing is done on day 3 if they request.

8 Adverse Events (AE) and Serious Adverse Events (SAE)

The wellbeing and safety of participants in this research is the paramount. Although a recent systemic analysis has not linked this procedure to any adverse events (AE) or serious adverse events (SAE),⁵ possible AE and their definition will be outlined below. Unexpected AE and SAE will also be monitored for and are defined below.

The investigators are responsible for the detection and documentation of AE or SAE as defined in this protocol. During the study, there will be a safety evaluation by the investigators in Mackay every month looking at AE. Any SAE is to be reported to the principal investigator within 24 hours. This will result in a safety evaluation of all current and past cases again and a report to the head of surgery and head of anaesthetics within 5 working days. Any time there is a SAE with definite or probable causality a report will be sent to the ethics committee and the trial may be suspended or terminated early at the principle investigator's, local head of department's or ethics committee's request.

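### The top two causality grades are inverted: reasonable timing alone earns 'Definitely', while 'Probable' needs timing, abatement and no other explanation, and section 8 hangs its safety trigger on these two grades

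*Protocol*

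**What the plan says.** Protocol section 8.4.2 has five grades. The three that matter here, from the top down, are:

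- 'Definitely': "The adverse event follows a reasonable temporal sequence from the time of study product administration or reappears when study product is reintroduced".
- 'Probable': reasonable timing, and in addition the event "abates upon discontinuation of the study product and cannot be reasonably explained by the known characteristics of the study Participant's clinical state".
- 'Possible': "The adverse event could have been caused by the study Participant's clinical state or the study product".

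The same section introduces the scale with "The investigators will use clinical judgment to determine the relationship" and asks that alternative causes be considered.

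The opening text of section 8 attaches a consequence to the top two grades: "Any time there is a SAE with definite or probable causality a report will be sent to the ethics committee". Suspension or early termination is then open to request by the principal investigator, a head of department or the ethics committee. Section 15.1 separately makes the principal investigator responsible for reporting serious adverse events (SAEs) to the ethics committee, with no causality condition.

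**The concern.** On a causality scale each step up should require stronger evidence. Here the highest step requires less than the one below it. Timing is also a weak discriminator in this trial: each participant has the laparotomy, the catheter insertion and the first ropivacaine dose in one theatre session, followed by 72 hours of boluses (sections 4 and 7.4). Most early post-operative events will follow all of these in a plausible sequence.

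At stake is a safety trigger that does not mean what its words suggest, and relationship data, recorded for each adverse event under section 8.3, in which the top grade carries little information. The abatement condition is borrowed from drug safety, whereas section 1 says the trial tests a technique rather than a drug. Needle damage to an abdominal organ, which section 8.1 makes an SAE, does not go away when an infusion stops.

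**Working it through.** The plan gives no figure to reproduce, so the check is logical. Section 8.4.2 uses four yes/no facts:

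- T: reasonable timing
- A: abates on discontinuation
- E: not reasonably explained by the clinical state
- R: reappears on reintroduction

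This gives 2 × 2 × 2 × 2 = 16 patterns.

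**As written**

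- Definitely = T or R. It fails only when both are absent, which is 4 patterns, so it covers 16 − 4 = 12.
- Probable = T and A and E. R is free, so it covers 2.
- Both 'Probable' patterns contain T, so both also meet 'Definitely'.
- The trigger (definite or probable) covers 12 of 16. It reduces to T or R, and the 'Probable' row adds nothing to it.

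**The decisive pattern.** Take T present and A, E and R absent: plausible timing, an ordinary explanation available, no abatement, no reappearance. It fails 'Probable' and meets 'Definitely'. It can also fit 'Possible', and the table does not say which of the two grades prevails.

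**For comparison, two stricter readings of the top row**

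| Top row | Definitely | Trigger |
|---|---|---|
| T or R (as printed) | 12 of 16 | 12 of 16 |
| T and R | 4 of 16 | 4 + 1 = 5 of 16 |
| T and A and E and R | 1 of 16 | 2 of 16 |

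In the second row, the added pattern is T, A and E without R.

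**Needle injury.** A and R cannot sensibly apply, so only T and E vary, giving 4 patterns. As written, 'Probable' covers 0 of 4 and 'Definitely' 2 of 4, one of which has another reasonable explanation. If T and E were both required, the condition would hold in 1 of 4.

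**Which SAEs reach the scale without a prior causality test.** Section 8.1 makes a catheter-site haematoma an SAE if it comes with a haemoglobin drop above 30 or a transfusion. It does the same for a wound infection leading to sepsis, a return to theatre or death. Neither needs a judgement on cause. Laparotomy can itself produce both, and both will usually satisfy T. For other, unlisted complications section 8.1 already requires a likely causal link before the event counts as an SAE.

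**The case against.** The strongest reply is that little follows in practice.

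- **Reporting.** A reader might infer that an injury graded only 'Possible' goes unreported. The documents do not support that. Section 8 sends any SAE to the principal investigator within 24 hours, then to a review of all cases and a report to both department heads, whatever its cause. Section 15.1 sends any SAE to the ethics committee. This stands. It also shows that sections 8 and 15.1 differ on whether the ethics report depends on causality.
- **Suspension.** It is discretionary, and section 9.4 allows termination on the number or severity of adverse events without reference to the causality grade. This stands: no automatic stop depends on the table.
- **Judgement.** Investigators weigh alternative causes, and 'Not Related' remains open to them. This makes wholesale misgrading unlikely. It does not repair the rows: 'Probable' states the alternative-explanation test and the higher grade omits it, so a careful assessor has to override the printed words.
- **Breadth.** A reader might infer that nearly every SAE would grade 'Definitely'. The causal filter on unlisted complications in section 8.1 rules out so general a claim.
- **Trial results.** A reader might also infer that relatedness by arm becomes uninterpretable. No endpoint in section 3 and no analysis in section 10.3 uses relatedness, and the complication endpoints carry no causality condition, so the arm comparisons are untouched.
- **What differs by arm.** It would be wrong to argue that only insertion differs. The infusion is delivered into a different plane in each arm (section 7.4), so infusion-related harms could differ too.

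**Conclusion.** The inversion is real and follows from the printed wording alone: 'Probable' is a strict subset of 'Definitely' (2 patterns within 12 of 16), and the section 8 trigger reduces to timing or reappearance. For the section 8.1 events listed without a causality test, the trigger as written does not separate related from unrelated events. 'Probable' is also out of reach for a needle injury.

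The consequence is modest: a redundant grade, a poorly discriminating trigger for a discretionary decision, and two ethics-reporting rules that do not match. Efficacy and complication comparisons are not affected.

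This rests on reading 'or' literally and on counting the laparotomy and its expected effects as part of the patient's clinical state. The pattern counts say nothing about how often such events will occur, and the protocol gives no rates from which to estimate that. The point is worth correcting because the amendment is small.

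**What to change.** Reword the two rows in section 8.4.2 so that 'Definitely' is at least as strict as 'Probable':

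- **Probable:** reasonable timing and no other reasonable explanation. Abatement on discontinuation is required in addition only for infusion-related events.
- **Definitely:** the same timing and no-other-explanation conditions, plus further confirming evidence. A raised local anaesthetic level should not count as that evidence by itself, because every participant receives ropivacaine and section 2 describes total concentrations just above reported thresholds in patients without signs or symptoms.

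Then reconcile the causality-conditional ethics report in section 8 with the unconditional one in section 15.1. Which rule should govern is for the sponsor and the ethics committee.

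The cost is a wording amendment to one table and alignment of two sentences, with ethics approval under section 15.6. Sample size and data collection do not change. Some early events will no longer grade as 'Definitely'.

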8.5 Follow-up of AEs and SAEs

All AEs and SAEs will be followed until resolution or until the Participant is lost to follow-up. Once resolved, the appropriate AE/SAE in the CRF will be updated. The investigator and treating doctors will ensure that follow-up will include any supplemental investigation, such as local anaesthetic blood levels, to help establish severity and/or causality of the AE or SAE.

9 Participant Completion and Discontinuation

9.1 Participant Completion

Having the rectus sheath catheters placed in theatre and receiving the Ropivacaine boluses for 72hrs whilst being monitored on ward round.

9.2 Stopping Rules / Discontinuation Criteria

Infection of the catheter/wound; Any SAE; Patient request

9.3 Participant Withdrawal

The patient is able to withdraw at any point. If they do they will be asked whether to withdraw from further data collection and whether they want their data already collected to be kept or discarded confidentially.

9.4 Early Termination of the Study

The study may be terminated prematurely by the principal investigator if:

- The number and/or severity of adverse events justify discontinuation of the study
- New data become available which raise concern about the safety of the study drug, so that continuation might cause unacceptable risks to participants.

After such a decision, all participating participants within two weeks will be notified as well as the Townsville Ethics Committee and chief medical officer of the MBH.

10 Data Analysis and Statistical Considerations

10.1 Hypotheses

Null hypothesis: Surgically placed pre-peritoneal catheters are superior to ultrasound placed rectus sheath catheters at reducing post-operative pain.

This hypothesis will be tested by the primary endpoint of total narcotic usage until day 3 post op and Patient blinded VAS scores at rest and coughing (0-10). These are both discussed below

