16.3	Regulatory Authorities.....	23
16.4	Informed Consent	24
16.6	Emergency Contact with Investigators.....	24
16.7	Notification of Primary Care Physician.....	24
16.10	Protocol Amendments	24
16.11	Protocol Compliance	24
16.12	Archives: Retention of Study Records	24
17	References.....	25

ABBREVIATIONS AND DEFINITIONS OF TERMS (examples only – modify as appropriate)

AE	Adverse Event
BMI	Body Mass Index (weight in kg divided by height in m ²)
BO	Bowels Open
CTN	Clinical Trial Notification
ECG	Electrocardiogram
IEC	Independent Ethics Committee
IV	Intravenous
Hr	Hour
MBH	Mackay Base Hospital
NHMRC	National Health and Medical Research Council
PI	Principal Investigator
®	Registered Product
ROP	Ropivacaine
SAE	Serious Adverse Event
SD	Standard Deviation
US	Ultrasound
UTI	Urinary Tract Infection
VAS	Visual analogue scale (Score of 1-10 for pain)
VTE	Venous Thromboembolism

Protocol Number: 1.02 Version 3

Protocol Title: Randomised single blinded trial of surgically placed pre-peritoneal vs ultrasound placed rectus sheath catheters post laparotomy

1 Synopsis

Study Title:

Randomised single blinded trial of surgically placed pre-peritoneal vs ultrasound placed rectus sheath catheters post laparotomy

Protocol Number:

1.02

Indication:

Patient undergoing a laparotomy (Emergency and Elective) under the general surgical team

Study Drugs:

Testing technique, not drugs. Both arms will then receive 20mL 0.2% Ropivacaine infusion through these catheters every 4 hrs for 3 days.

No. Participants:

72 Patients

No. Centres:

1 Centre; Mackay Base Hospital

Study Duration:

Approximately 1 year

Objectives of the Study:

The goal of this project is to prove if surgically placed pre-peritoneal catheters are more effective than ultrasound placed rectus sheath catheters at improving post-operative pain.

Study Endpoints:

The primary endpoint is:

- Total narcotic usage until day 3 post op. This will be measured in mg of IV Morphine. All other narcotic agents (Oral or IV) will be calculated back to IV Morphine equivalence as per dosage equivalence on MIMs.

Secondary endpoints:

- Time taken for procedure (Minutes)
- Patient blinded VAS scores at rest and coughing (0-10)
- Time till flatus (Days)
- Time till BO (Days)
- Time till discharge (Days)
- Complications
 - o Wound infection
 - o UTI
 - o VTE

Study Design:

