All enrolled patient will be randomised into two even arms via random allocation sequence in numbered envelopes. A third party doctor using computer randomisation will conduct the randomisation prior to commencement of the project. The allocation will be revealed prior to closure of the abdomen where the patient will either receive a surgically placed pre-peritoneal catheter or an ultrasound guided rectus sheath catheter inserted by the anaesthetic team prior to waking up from the general anaesthetic.

These catheters will then be intermittently infused with local anaesthetic over the next 72 hours via a pump. Over this time the patients' opiate analgesic requirement and the visual analogue scale (VAS) will be monitored daily. The surgical team and the anaesthetic pain team will review the patients daily for the above and monitor for adverse effects from the procedure/local anaesthetic.

Eligibility Criteria (Inclusion and Exclusion)

Inclusion: All adult general surgical patients undergoing a midline laparotomy at Mackay base hospital

Exclusion Criteria:

- Local Anaesthetic allergy
- Catheter plastic allergy
- Multiple operations as defined as alteration of anatomy of the abdominal wall, preventing placement of catheters.
- Chronic abdominal pain as defined as abdominal pain with opiate use for > 12 weeks
- Abdomen left open
- Patient under 18 years of age
- Pregnant
- Inability of surgical/anaesthetic staff to perform procedure
- Patients with altered cognition (dementia or delirium) and therefore unable to respond to

VAS.

- Patients intubated & therefore unable to communicate

Sample Size Determination:

Calculation of the sample size was performed by using the primary endpoint of 72-hour total morphine usage post laparotomy. In a similar previous study, the total dose of administered morphine was 62mg with a standard deviation of 16mg.⁴ It was decided that a difference of 20% (12mg) would be considered clinically relevant, similar to this previous study.

Assuming $\alpha = 0.05$ and $\beta = 0.15$ (a power of 85 per cent), a total of 66 patients (33 patients per group) would be required to find there was no difference between each group¹⁰. Assuming a 10% dropout rate 72 patients need to be recruited (36 patients per group) to make this number.

2 Introduction

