In this study, the catheters will be inserted and secured by either a surgical or anaesthetic consultant. Surgical consultants and anaesthetic consultants will be orientated to the standard specified procedure (as detailed in section 7.4 of this protocol) of placement as led by [name] (Director of Surgery) prior to the commencement of this study.

3 Objectives

Null hypothesis: Surgically placed pre-peritoneal catheters are superior to ultrasound placed rectus sheath catheters at reducing post-operative pain.

The primary endpoint is:

- Total narcotic usage until day three post op. This will be measured in mg of IV Morphine. All other narcotic agents (Oral or IV) will be calculated back to IV Morphine equivalence as per dosage equivalence on MIMs.

Secondary endpoints:

- Time taken for procedure (Minutes)
- Patient blinded VAS scores at rest and coughing (0-10)
- Time till flatus (Days)
- Time till BO (Days)
- Time till discharge (Days)
- Complications
 - o Wound infection
 - o UTI
 - o VTE

4 Study Design

This will be a randomised, patient blinded trial. All enrolled patient will be randomised into 2 even arms – One to receive a surgically placed pre-peritoneal catheter, the other an ultrasound guided rectus sheath catheter inserted by the anaesthetic team prior to waking up from the general anaesthetic. Both will then receive 72 hours of intermittent Ropivacaine 0.2% boluses via these catheters.

Patients will be screened for the study when they are booked up for an emergency or elective procedure which will always or potentially require a midline laparotomy. These patients will then be consented for potential enrolment. Enrolment and allocation will be only revealed when it is sure that the patient does not meet any of the exclusion criteria in theatre prior to closure of the abdomen via randomised numbered envelopes.

These numbered envelopes will be generated prior to the start of the study by a 3rd party doctor. This doctor, who is not involved in the study in any other way, will use a random allocation sequence generated by computer using non-blocking randomisation.

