10.3 Statistical Analysis

All analysis will be performed by a qualified statistician at TTH. The first analysis will be to investigate if there are any significant difference between the demographics and primary clinical characteristics of each arm using Student's *t*-test or Fisher's exact test as appropriate.

Repeated measurements (pain scores) will be analysed by repeated measures ANOVA or ANOVA on ranks, with further paired comparisons at each time interval performed using the *t*-test or Mann–Whitney *U*-test as appropriate. Categorical data will be analysed using χ^2 analysis or Fisher's exact test where applicable. Normally distributed data such as morphine usage will be presented as means \pm sd of the mean, non-normally distributed data are presented as medians \pm quartiles (interquartile range), and categorical data are presented as raw data and as frequencies. Other testing may be done at the statistician's discretion.

The α level for all analyses was set as $P < 0.05$. The endpoints will then be analysed for any statistically significant differences. The arms will not be broken down further by demographics or primary clinical characteristics due to the small size likely causing spurious results.

If there is a false reading (eg morphine usage of 600mg instead of what was likely 60mg); the data and collection tools will be audited again. If the discrepancy cannot be found the patient result may be left out of the analysis, but will be clearly outlined that they were excluded and why in the report. Similarly, if there is missing information, the patient's result may be left out of the analysis, but will be clearly outlined why they were excluded in the report.

11 Data Management

The data collection sheets as well as the patient's electronic notes will be used to collect the data at first. Once a full data set for the patient is complete (Minimum of 2 months post procedure to record any late complications in the follow up), the data will then be completely de-identified and placed on a password protected excel spreadsheet. This will be audited by an independent surgical registrar. Once this is audited, the data collection tool and any re-identifiable materials will be disposed in confidential waste bins. This password protected completely de-identified spreadsheet will be kept on a private QH drive and the investigators personal drive to ensure 2 copies. This data will be kept for the minimum 15 years required.

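### Section 10.1 lets VAS at rest and on coughing test the superiority hypothesis beside opioid use, although VAS is secondary elsewhere and the trial is sized on morphine alone

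*Protocol*

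**What the plan says.** The synopsis gives one primary endpoint: "Total narcotic usage until day 3 post op. This will be measured in mg of IV Morphine". Section 3 repeats it: "Total narcotic usage until day three post op. This will be measured in mg of IV Morphine". In both places VAS at rest and on coughing appears in the list of secondary endpoints.

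The sample size follows the same line. The synopsis says it was calculated "using the primary endpoint of 72-hour total morphine usage post laparotomy". Section 10.2 also uses total morphine, and describes the 85% power only in terms of a reduction in narcotic use. Neither place sizes VAS.

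Section 10.1 departs from this. It states a single hypothesis, about superiority of the surgical catheter in reducing pain, and says it will be "tested by the primary endpoint of total narcotic usage until day 3 post op and Patient blinded VAS scores at rest and coughing".

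Section 10.3 does not resolve the difference. The α "level for all analyses was set as $P < 0.05". Pain scores get a repeated measures ANOVA or an ANOVA on ranks, "with further paired comparisons at each time interval performed using the" t-test or Mann–Whitney U-test. It adds: "The endpoints will then be analysed for any statistically significant differences". Further tests are left to the statistician's discretion.

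**The concern.** One hypothesis is attached to three outcomes (opioid use, VAS at rest, VAS on coughing), each tested at 0.05, and the protocol does not say whether one, some or all must be significant. Two sections make VAS supportive; the section that governs the test makes it part of the decision.

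The consequence depends on how section 10.1 is read. If any one outcome suffices, the chance of a false claim rises. If all are needed, the chance of a true claim falls below what the sample size promises. Opioid use and VAS can also disagree, because patients take opioid in response to pain: an arm could show less pain with more opioid. As written, such a result could be reported as success or as failure.

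**Working it through.** **Inputs from the protocol.** Mean 62 mg, SD 16 mg, relevant difference 20% (written as 12 mg; exactly 20% of 62 is 12.4 mg), α = 0.05, power 85% (synopsis and section 10.2). Outcomes named for the hypothesis: three (section 10.1). VAS schedule: rest and coughing on days 1, 2 and 3 (table in section 6.2). Correlations between outcomes are not given; the values below are assumptions.

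**Step 1: reproduce the stated sample size.** Per group, n = 2(z₀.₉₇₅ + z₀.₈₅)² × SD² / δ², with (1.960 + 1.036)² ≈ 8.98.
- δ = 12: 2 × 8.98 × 256 / 144 ≈ 31.9, so 32 per group; 33 with the t distribution (66 in total, the synopsis figure).
- δ = 12.4: 2 × 8.98 × 256 / 153.76 ≈ 29.9, so 30 per group; 31 with the t distribution (62 in total, the section 10.2 figure).
- One-sided 0.05 gives 52 or 48 in total and matches neither.

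Both stated totals are therefore the size for one endpoint at two-sided 0.05. (That the two passages differ is a separate matter.)

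**Step 2: any one of three outcomes suffices, each at 0.05.** With no true difference on any outcome:
- Either direction, independent: 1 − 0.95³ = 0.143.
- Favouring the surgical catheter only, independent: 1 − 0.975³ = 0.073. One endpoint gives 0.025.
- With a common correlation (simulated normal test statistics, 1,000,000 draws):

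| Assumed correlation | Either direction | Favouring surgical catheter |
|---|---|---|
| 0 | 14.3% | 7.3% |
| 0.3 | 13.6% | 6.8% |
| 0.5 | 12.5% | 6.3% |
| 0.7 | 10.9% | 5.5% |

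**Step 3: all three must succeed.** Type I error does not exceed that of a single test. Power cannot exceed the power for opioid use, which is 85% by design, and falls below it unless VAS is certain to succeed whenever opioid use does. The protocol gives no VAS effect or SD, so the loss cannot be computed. As an illustration only: three independent outcomes with 85% power each would give 0.85³ = 0.61.

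**Step 4: cost of keeping three routes.** With Bonferroni, α = 0.05/3 = 0.0167 for each outcome. For opioid use, n = 2(2.394 + 1.036)² × 256 / 144 ≈ 41.8, so 42 per group, 84 evaluable in total (80 at 12.4 mg). The like-for-like normal-approximation figure for one endpoint is 64 (60 at 12.4 mg). With 33 per group, opioid power at 0.0167 would be 74.3% at 12 mg (77.5% at 12.4 mg).

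**The case against.** The best defence is that the intended hierarchy can be recovered. Section 10.1 itself attaches the singular term primary endpoint to narcotic use, two sections list VAS as secondary, and the sizing uses morphine only, so section 10.1 is the outlier. A multiplicity method may also stand in a statistical analysis plan. Both points have weight, and the absence of a multiplicity method is not the complaint. What remains is that the protocol contradicts itself on the role of VAS, and an analysis plan would have to override one section or the other.

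A reader might go further in three ways that the document does not support.

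- **That the protocol permits a claim on any outcome as a rule.** It joins the outcomes with the word and, and states no rule. The error rates in step 2 apply to one possible reading.
- **That the false-positive chance is about 30%.** This is 1 − 0.95⁷ = 0.302, from opioid use plus six daily VAS comparisons. It treats the daily comparisons as independent, stand-alone routes to success. Section 10.3 presents them as follow-up to the repeated measures analysis, and pain scores from the same patient are unlikely to be independent.
- **That the opioid window biases the primary result.** The window appears both as until day 3 and as 72 hours (synopsis sample size; section 4 also speaks of the first 72 hours). But no ward-round cut-off for opioid is stated, and section 6.2.2 lets totals be derived afterwards from the medication chart. Hour of surgery should be balanced by randomisation, so a loose cut-off would add mainly noise. This is a wording alignment only.

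**Conclusion.** The contradiction is real and should be corrected: the protocol makes VAS secondary in two sections and part of the hypothesis test in a third, with 0.05 for every analysis and a sample size for opioid use alone.

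If any one of the three outcomes suffices, the two-sided familywise error is up to 14.3% (about 12.5% at correlation 0.5). The error that matters for a superiority claim, a false result favouring the surgical catheter, is about 5.5% to 7.3% instead of 2.5%. The ranges rest on assumed common correlations from 0 to 0.7 and on no true difference in any outcome. If all must succeed, the error rate is sound, but the stated 85% power no longer describes the trial. The protocol does not say which reading applies.

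**What to change.** Reword section 10.1 to say that superiority is judged only on total IV-morphine-equivalent use, tested at 0.05. State there and in section 10.3 that VAS at rest and on coughing, including the comparisons at each time interval, is secondary and supportive and cannot by itself support a superiority claim. This agrees with the synopsis, section 3 and the sample size. It leaves alpha and N unchanged; the only cost is losing the option of claiming success on VAS alone. If the sponsor does want VAS to count, the protocol must state the rule and size for it (step 4 shows the price of one such rule).

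As a minor alignment, define the primary window once, reconciling the day 3 and 72-hour wordings, and start the clock at a point common to both arms, such as end of surgery. The first catheter bolus is not suitable: under section 7.4 it comes before the abdominal wall is closed in the surgical arm and after closure in the ultrasound arm. A window starting there would cover less postoperative time in the surgical arm.
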